**Table 6-21 Fatigue/asthenia suspected to be related to capmatinib**

Grade (CTCAE v5)	Mandatory dose modification
Grade 3	Interrupt capmatinib until resolved to Grade $\leq 1$ 
 
• If resolved in <math>\leq 7</math> days, restart at same dose level
 
• If not resolved within 7 days, restart at reduced dose level
 

Grade 4	Permanently discontinue capmatinib

**Table 6-22 Peripheral edema suspected to be related to capmatinib**

Grade (CTCAE v5)	Mandatory dose modification
Grade 3	Interrupt capmatinib until resolved to grade $\leq 1$ , then restart at reduced dose level

Grade (CTCAE v5)	Mandatory dose modification
Grade 4	Permanently discontinue capmatinib

**Table 6-23 Other adverse events suspected to be related to capmatinib**

Grade (CTCAE v5)	Mandatory dose modification
Grade 1 or 2	Maintain dose level of capmatinib, consider initiating appropriate support medication For any intolerable grade 2 (e.g. limiting instrumental ADL), consider interrupting the dose until resolved to grade $\leq$ 1, then restart at reduced dose level
Grade 3	Interrupt capmatinib until resolved to grade $\leq$ 2, then restart at reduced dose level
Grade 4	Permanently discontinue capmatinib
Myocarditis (any grade) or other cardiac events Grade $\geq$ 3	Permanently discontinue capmatinib (refer to Table 14-17 for recommended management guidelines for those events)

### 6.3.1.5 Mandatory dose modifications for canakinumab

**Table 6-24 Infections suspected to be related to canakinumab**

Grade (CTCAE v5)	Mandatory dose modifications
Grade 3	Interrupt canakinumab until resolved to $\leq$ grade 2, then restart at the same dose level
Grade 4	Permanently discontinue canakinumab

**Table 6-25 Hematological adverse events suspected to be related to canakinumab**

Grade (CTCAE v5)	Mandatory dose modification
Neutropenia	
Grade 3 (ANC < 1000 - 500/mm  )	Interrupt canakinumab until resolved to $\leq$ grade 2, then restart at the same dose level
Grade 4 (ANC < 500/mm  )	Permanently discontinue canakinumab
Febrile neutropenia	
ANC < 1.0 $\times$ 10  /L, fever $\geq$ 38.5°C	Permanently discontinue canakinumab
Thrombocytopenia	
Grade 3 (< 50,000 - 25,000/mm  )	Interrupt canakinumab until resolved to $\leq$ grade 1 
 
• If resolved in <math>\leq</math> 7 days, restart at same dose
 
• If not resolved within 7 days, permanently discontinue canakinumab
 

Grade 4 (< 25,000/mm  )	Permanently discontinue canakinumab

**Table 6-26 Creatinine alterations suspected to be related to canakinumab**

Grade (CTCAE v5)	Mandatory dose modification
Grade 3 (> 3.0 - 6.0 $\times$ ULN; or >3.0 $\times$ baseline if baseline was elevated)	Interrupt canakinumab until resolved to $\leq$ grade 2 or baseline 
 
• If resolved in <math>\leq</math> 14 days, then restart at the same dose level
 
• If not resolved within 14 days, permanently discontinue canakinumab
 

Grade 4 (> 6.0 $\times$ ULN)	Permanently discontinue canakinumab

**Table 6-27 Hepatic adverse events suspected to be related to canakinumab**

Grade (CTCAE v5)	Mandatory dose modifications
Isolated total Bilirubin elevation	
Grade 2 (> 1.5 - 3.0 $\times$ ULN; >1.5 - 3.0 $\times$ baseline if baseline was abnormal)	Interrupt canakinumab and monitor liver test a weekly, or more frequently if clinically indicated, until resolved to $\leq$ 1.5 $\times$ ULN 
 
• If resolved in <math>\leq</math> 14 days, restart at same dose level
 

Grade (CTCAE v5)	Mandatory dose modifications
	
 
• If not resolved within 14 days, permanently discontinue canakinumab
 

Grade 3 (> 3.0 - 10.0 × ULN*; >3.0 - 10.0 x baseline if baseline was abnormal)	Interrupt canakinumab and monitor liver test a weekly, or more frequently if clinically indicated, until resolved to ≤ 1.5 × ULN 
 
• If resolved in ≤ 14 days, then restart at the same dose level
 
• If not resolved within 14 days, permanently discontinue canakinumab. The subject should be monitored weekly (including liver testa), or more frequently if clinically indicated, until total bilirubin have resolved to baseline or stabilization over 4 weeks.
 

Grade 4 (> 10.0 × ULN*; >10.0 x baseline if baseline was abnormal)	Permanently discontinue canakinumab. The subject should be monitored weekly (including liver test a ), or more frequently if clinically indicated, until total bilirubin have resolved to baseline or stabilization over 4 weeks.
Isolated AST or ALT elevation	
Grade 2 (> 3.0 - 5.0 × ULN; >3.0 - 5.0 x baseline if baseline was abnormal)	Continue canakinumab at the same dose level Repeat liver test a within 48-72 hours; if abnormal values are confirmed upon the repeat test, then monitor liver test a weekly, or more frequently if clinically indicated, until resolved to ≤ 3.0 × ULN
Grade 3 > 5.0 - 10.0 × ULN; >5.0 – 10 x baseline if baseline was abnormal	Interrupt canakinumab. Repeat liver test a within 48-72 hours; monitor liver test a weekly, or more frequently if clinically indicated, until resolved to ≤ 3.0 × ULN. 
 
• If resolved in ≤ 28 days, restart canakinumab at same dose
 
• If not resolved within 28 days, permanently discontinue canakinumab
 

> 10.0 - 20.0 × ULN* >10 - 20 x baseline if baseline was abnormal	Permanently discontinue canakinumab Repeat liver test a within 48-72 hours. Monitor liver test a weekly, or more frequently if clinically indicated, until resolved to ≤ baseline
Grade 4 (> 20.0 × ULN; >20.0 x baseline if baseline was abnormal)	Permanently discontinue canakinumab Repeat liver test a within 48-72; monitor liver test a weekly, or more frequently if clinically indicated, until resolved to ≤ 3 × ULN
Combinedb elevations of AST or ALT and total bilirubin	
For subjects with normal baseline ALT and AST and total bilirubin value: AST or ALT >3.0 × ULN combined with total bilirubin >2.0 × ULN without evidence of cholestasis c	Permanently discontinue canakinumab Repeat liver test a within 48-72; monitor liver test a weekly or more frequently if clinically indicated, until AST, ALT, or bilirubin have resolved to baseline or stabilization over 4 weeks.

aCore liver tests consist of ALT, AST, GGT, total bilirubin (fractionated [direct and indirect], if total bilirubin > 2.0 × ULN), and alkaline phosphatase (fractionated [quantification of isoforms], if alkaline phosphatase > 2.0 × ULN.)
 
b“Combined” defined as total bilirubin increase to the defined threshold concurrently with ALT/AST increase to the defined threshold. If combined elevations of AST or ALT and total bilirubin do not meet the defined thresholds, please follow the instructions for isolated elevation of total bilirubin and isolated elevation of AST/ALT, and take a conservative action based on the degree of the elevations (e.g. discontinue treatment at the situation when omit dose is needed for one parameter and discontinue treatment is required for another parameter). After all elevations resolve to the defined thresholds that allow treatment re-initiation, re-start the treatment either at the same dose or at one dose lower if meeting a criterion for dose reduction.
 
c“Cholestasis” defined as ALP elevation (>2.0 × ULN and R value <2 ) in subjects without bone metastasis, or elevation of ALP liver fraction in subjects with bone metastasis. Note: The R value is calculated by dividing the ALT by the ALP, using multiples of the ULN for both values. It denotes whether the relative pattern of ALT and/or ALP elevation is due to cholestatic (R ≤ 2), hepatocellular (R ≥ 5), or mixed (R >2 and < 5) liver injury.
 
* If total bilirubin > 3.0 × ULN is due to the indirect (non-conjugated) component only, and hemolysis as the etiology has been ruled out as per institutional guidelines (e.g., review of peripheral blood smear and haptoglobin determination), continue treatment at the discretion of the investigator.
	

**Table 6-28 Pancreatitis, amylase and/or lipase elevations suspected to be related to canakinumab**

Grade (CTCAE v5)	Mandatory dose modification
Pancreatitis	
Grade ≥ 3	Permanently discontinue canakinumab
Asymptomatic amylase and/or lipase elevation*	
Grade 3 (> 2.0 - 5.0 x ULN with signs or symptoms; >5.0 x ULN and asymptomatic)	Interrupt canakinumab until resolved to grades ≤ 1 or baseline 
 
• If resolved in ≤ 7 days, restart at same dose level
 
• If not resolved within 7 days, permanently discontinue canakinumab
 

Grade 4 (> 5.0 x ULN and with signs or symptoms)	Permanently discontinue canakinumab
*A CT scan or other imaging study to assess the pancreas, liver, and gallbladder must be performed within 1 week of the first occurrence of any ≥ Grade 3 of amylase and/or lipase. If asymptomatic Grade 2 elevations of lipase and/or amylase occur again at the reduced dose, subjects will be discontinued permanently from study treatment.	

**Table 6-29 Hypertension suspected to be related to canakinumab**

Grade (CTCAE v5)	Mandatory dose modification
Grade 3	Interrupt canakinumab until resolved ≤ grade 1, then restart at same dose level
Grade 4	Permanently discontinue canakinumab

**Table 6-30 Diarrhea suspected to be related to canakinumab**

Grade (CTCAE v5)	Mandatory dose modifications
Grade 2	Interrupt canakinumab until resolved to ≤ Grade1, then restart at same dose level
Grade 3	Permanently discontinue canakinumab
Grade 4	Permanently discontinue canakinumab

**Table 6-31 Skin related toxicities suspected to be related to canakinumab**

[figure not shown]
Grade (CTCAE v5)	Mandatory dose modification
Grade 3, despite skin toxicity therapy	Interrupt canakinumab until resolved to Grades ≤ 1 
 
• If resolved in ≤ 7 days, restart at same dose level
 
• If not resolved within 7 days (despite appropriate skin toxicity therapy), permanently discontinue canakinumab
 

Grade 4, despite skin toxicity therapy	Permanently discontinue canakinumab

**Table 6-32 Fatigue/asthenia suspected to be related to canakinumab**

Grade (CTCAE v5)	Mandatory dose modifications
Grade 3	Interrupt canakinumab until resolved to ≤ grade1 
 
• If resolved in ≤ 14 days, restart at same dose level
 
• If not resolved within 14 days, permanently discontinue canakinumab
 

**Table 6-33 Other adverse events suspected to be related to canakinumab**

Grade (CTCAE v5)	Mandatory dose modification
Grade 3	Interrupt canakinumab until resolved to ≤ grade 1, restart at the same dose level
Grade 4, except alopecia	Permanently discontinue canakinumab

### 6.3.1.6 Mandatory dose modifications for ribociclib

**Table 6-34 Hematological adverse events suspected to be related to ribociclib**

Grade (CTCAE v5)	Mandatory dose modification
Thrombocytopenia	
Grade 2 ( $\geq 50 \times 10^9/L$ – $< 75 \times 10^9/L$ )	Dose interruption until recovery to grade $\leq 1$ . Re-initiate ribociclib at the same dose.
Grade 3 ( $\geq 25 \times 10^9/L$ – $< 50 \times 10^9/L$ )	Dose interruption until recovery to grade $\leq 1$ . Re-initiate ribociclib at the same dose level. If toxicity recurs at grade 3: temporary dose interruption until recovery to grade $\leq 1$ and reduce ribociclib to the next lower dose level.
Grade 4 ( $< 25 \times 10^9/L$ )	Dose interruption until recovery to grade $\leq 1$ . Re-initiate ribociclib at the next lower dose level. If toxicity recurs at grade 4: discontinue ribociclib
Absolute neutrophil count (ANC)	
Grade 3 ( $\geq 0.5 \times 10^9/L$ – $< 1.0 \times 10^9/L$ )	Dose interruption until recovery to $\geq 1.0 \times 10^9/L$ . Re-initiate ribociclib at the same dose level. If toxicity recurs at grade 3: temporary dose interruption until recovery to $\geq 1.0 \times 10^9/L$ . If resolved in $\leq 7$ days, then maintain dose level. If resolved in $> 7$ days, then reduce ribociclib dose to the next lower dose level.
Grade 4 ( $< 0.5 \times 10^9/L$ )	Dose interruption until recovery to $\geq 1.0 \times 10^9/L$ . Re-initiate ribociclib at the next lower dose level.
Febrile neutropenia	
Grade 3 ANC $< 1.0 \times 10^9/L$ with a single temperature of $> 38.3$ °C (101 °F) or a sustained temperature of $\geq 38$ °C (100.4 °F) for more than one hour	Dose interruption until improvement of ANC $\geq 1.0 \times 10^9/L$ and no fever. Restart at the next lower dose level. If febrile neutropenia recurs, discontinue ribociclib.
Grade 4 Life-threatening consequences; urgent intervention indicated	Discontinue ribociclib.
Anemia (Hemoglobin)	
Grade 3 ( $< 8.0$ g/dL)	Dose interruption until recovery to grade $\leq 2$ . Re-initiate ribociclib at the same dose.
Grade 4 Life-threatening consequences; urgent intervention indicated	Discontinue ribociclib.

**Table 6-35 Abnormal liver tests suspected to be related to ribociclib**

Grade (CTCAE v5)	Mandatory dose modification
TOTAL BILIRUBIN without ALT/AST increase above baseline value	
Grade 1 ( $> ULN$ – $1.5 \times ULN$ ) (confirmed 48-72h later)	No dose adjustment required with LFTs monitored every 2 weeks
Grade 2 ( $> 1.5$ – $3.0 \times ULN$ )	Dose interruption of ribociclib If resolved to $\leq$ grade 1 in $\leq 21$ days, then maintain dose level If resolved to $\leq$ grade 1 in $> 21$ -28 days or toxicity recurs, then reduce to the next lower dose level Repeat liver enzyme and bilirubin tests twice weekly for 2 weeks after dose resumption

	If toxicity recurs after two dose reductions, or recovery to $\leq$ grade 1 is $>$ 28 days, discontinue ribociclib
Grade 3 ( $>$ 3.0 – 10.0 x ULN)	Dose interruption of ribociclib, until resolved to $\leq$ grade 1, then reduce to the next lower dose level Repeat liver enzyme and bilirubin tests twice weekly for 2 weeks after dose resumption If resolved to $\leq$ grade 1 in $>$ 28 days or toxicity recurs, discontinue ribociclib
Grade 4 ( $>$ 10.0 x ULN)	Discontinue ribociclib

Confounding factors and/or alternative causes for increase of total bilirubin should be excluded before dose interruption/reduction. They include but are not limited to: evidence of liver metastases, evidence of obstruction, such as elevated ALP and GGT typical of gallbladder or bile duct disease, hyperbilirubinemia due to the indirect component only (i.e. direct bilirubin component <math>\leq</math> 1 x ULN) due to hemolysis or Gilbert Syndrome, other pharmacologic treatment, viral hepatitis, alcoholic or autoimmune hepatitis, other hepatotoxic drugs.
 
For patients with Gilbert Syndrome, these dose modifications apply to changes in direct bilirubin only. Bilirubin will be fractionated if elevated.
	
AST or ALT without bilirubin elevation <math>></math> 2 x ULN	
Same grade as baseline or increase from baseline grade 0 to grade 1 (confirmed 48 – 72 h later)	No dose adjustment required with LFTs monitored per protocol if same grade as baseline or every 2 weeks in case of increase from baseline grade 0 to 1
Increase from baseline grade 0 or 1 to grade 2 ( $>$ 3.0 – 5.0 x ULN)	Dose interruption of ribociclib If resolved to $\leq$ baseline grade in $\leq$ 21 days, then maintain dose level If resolved to $\leq$ baseline grade in $>$ 21 days or toxicity recurs, then reduce to the next lower dose level Repeat liver enzyme and bilirubin tests twice weekly for 2 weeks after dose resumption If toxicity recurs after two dose reductions or recovery to $\leq$ baseline grade is $>$ 28 days, discontinue ribociclib
Increase from baseline grade 0 or 1 to grade 3 ( $>$ 5.0 – 20.0 x ULN)	Dose interruption of ribociclib until resolved to $\leq$ baseline grade, then reduce to the next lower dose level Repeat liver enzyme and bilirubin tests twice weekly for 2 weeks after dose resumption If recovery to $\leq$ baseline grade is $>$ 28 days, discontinue ribociclib If toxicity recurs, discontinue ribociclib
Increase from baseline grade 2 to grade 3 ( $>$ 5.0 – 20.0 x ULN)	Dose interruption of ribociclib until resolved to $\leq$ baseline grade, then reduce to the next lower dose level Repeat liver enzyme and bilirubin tests twice weekly for 2 weeks after dose resumption If toxicity recurs after two dose reductions or recovery to $\leq$ baseline grade is $>$ 28 days, discontinue ribociclib.
Grade 4 ( $>$ 20.0 x ULN)	Discontinue ribociclib
AST or ALT and concurrent Bilirubin	

For patients with normal ALT and AST and total bilirubin at baseline: AST or ALT <math>></math>3.0 x ULN combined with total bilirubin <math>></math> 2 x ULN without evidence of cholestasis
 
OR
 
For patient with elevated AST or ALT or total bilirubin at baseline: [AST or ALT <math>></math>2 x baseline AND <math>></math>3.0x ULN] OR [AST or ALT <math>></math> 8.0 x ULN]- whichever is lower- combined with [total bilirubin <math>></math> 2 x baseline AND <math>></math>2.0 x ULN]
	Discontinue ribociclib

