	
b If total bilirubin > 3.0 x ULN is due to the indirect (non-conjugated) component only, and hemolysis as the etiology has been ruled out as per institutional guidelines (e.g. review of peripheral blood smear and haptoglobin determination), then ↓ 1 dose level and continue treatment at the discretion of the Investigator.
 
c 'Cholestasis' defined as: ALP elevation (> 2 x ULN and R value (ALT/ALP in x ULN) < 2) in patients without bone metastases, or elevation of ALP liver fraction in patients with bone metastases. Note: The R value is calculated by dividing the ALT by the ALP, using multiples of the ULN for both values. It denotes whether the relative pattern of ALT and/or ALP elevation is due to cholestasis (R≤2), hepatocellular (R≥5), or mixed (R>2 and <5) liver injury.
 
d If combined elevations of AST or ALT and total bilirubin do not meet the defined thresholds, please follow the instructions for isolated elevation of AST/ALT, and take a conservative action based on the degree of the elevations (e.g., discontinue treatment at the situation when omit dose is needed for one parameter and discontinue treatment is required for another parameter). After all elevations resolve to the defined thresholds that allow treatment re-initiation, re-start treatment either at the same dose or one dose lower if meeting a criterion for dose reduction.

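### Table 6-35 (ribociclib) gives no row, or a milder row, for some combined rises in bilirubin and ALT/AST

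*Protocol*

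**What the plan says.** Table 6-35 (Protocol Section 6.3.1.6) has three blocks, each with its own entry condition.

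- **Bilirubin rows**, headed "TOTAL BILIRUBIN without ALT/AST increase above baseline value". Grade 1 (above ULN to 1.5 x ULN) needs no dose change. Grade 2 (above 1.5 to 3.0) means interrupt. Grade 3 (above 3.0 to 10.0) means interrupt, then reduce. Grade 4 means discontinue. A note under these rows asks that other causes, biliary obstruction among them, be excluded before the dose is interrupted or reduced.
- **ALT/AST rows**, headed "AST or ALT without bilirubin elevation" with the limit set at >2 x ULN. The first row covers an unchanged grade or a move from grade 0 to 1: "No dose adjustment required with LFTs monitored per protocol if same grade as baseline", or every two weeks after a move from 0 to 1.
- **Combined row**, headed "AST or ALT and concurrent Bilirubin": discontinue. At normal baseline it needs ALT or AST >3 x ULN and bilirubin >2 x ULN, "without evidence of cholestasis". At elevated baseline it needs ALT or AST above both 2 x baseline and 3 x ULN, or above 8 x ULN, with bilirubin above both 2 x baseline and 2 x ULN.

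The tables for two other study drugs carry a bridging note. Table 6-27 footnote b (canakinumab) begins "If combined elevations of AST or ALT and total bilirubin do not meet the defined thresholds" and continues "please follow the instructions for isolated elevation of total bilirubin and isolated elevation of AST/ALT". Table 6-15 footnote d (capmatinib) says "please follow the instructions for isolated elevation of AST/ALT, and take a conservative action based on the degree of the elevations", naming only the AST/ALT rows. Table 6-35 has no bridging note.

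Section 6.3.1 forbids deviation from mandatory interruptions and reductions, bases modifications on the worst preceding toxicity, and sends an unlisted event to the guideline for other adverse events (Table 6-37 for ribociclib). Table 6-2 assigns hepatic events on ribociclib to Table 6-35.

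**The concern.** A mandatory dosing table should give one action for every liver picture it is meant to govern. Here the entry conditions remove a patient from the bilirubin rows as soon as ALT/AST moves above baseline, and from the ALT/AST rows as soon as bilirubin passes 2 x ULN. The combined row does not pick up everyone who has been removed. In one range a worse liver picture also meets a milder instruction than bilirubin alone.

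What is at stake is patient safety and consistent dosing between sites. The pattern is foreseeable. In the phase I study of this combination summarised in Section 1.2.5.2.2, related ALT increases occurred in 6 of 10 patients, AST increases in 3 and a bilirubin increase in 1. Exclusion criterion 34 also admits subjects with liver metastasis and ALT just below 5 x ULN.

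**Working it through.** No sample size or error rate is involved, so the check is logical: apply each block's entry condition to given values and see which rows match. All values are multiples of ULN. Three assumptions are made. ALT grades follow the ULN multiples printed in the table (grade 1 up to 3, grade 2 up to 5, grade 3 up to 20). Baseline bilirubin is normal, since criterion 34 excludes bilirubin at or above ULN except in Gilbert's syndrome. ALT stands for ALT or AST.

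**Matching rows**

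| Baseline ALT | ALT | Bilirubin | Cholestasis | Rows matched |
|---|---|---|---|---|
| 0.8 | 0.8 | 1.8 | no | Bilirubin grade 2 (interrupt) and ALT same grade (no change): conflict |
| 4 | 4 | 1.8 | no | The same conflict |
| 0.8 | 2.5 | 1.8 | no | ALT grade 0 to 1 only: no change |
| 2 | 2.8 | 1.8 | no | ALT same grade only: no change |
| 4 | 4.8 | 1.8 | no | ALT same grade only: no change |
| 0.8 | 2.5 | 2.5, 5 or 11 | no | None |
| 4 | 6 | 5 | no | None |
| 4 | 8.1 | 5 | no | Combined: discontinue |
| 0.8 | 5 | 4 | no | Combined: discontinue |
| 0.8 | 5 or 12 | 4 | yes | None |

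**Width of the sub-threshold gap (bilirubin above 2).** At normal baseline it runs from above baseline up to ALT 3. For an elevated baseline ALT b, the combined row starts above min(max(3, 2b), 8), so the gap runs from above b to that value:

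- b = 2: max(3, 4) = 4, so above 2 to 4.
- b = 2.5: above 2.5 to 5.
- b = 3: above 3 to 6.
- b = 4: above 4 to 8.
- b = 4.9: 2b = 9.8, capped at 8, so above 4.9 to 8.

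Under criterion 34, values of b from 2.5 up to below 5 occur only with liver metastasis.

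**Does Table 6-37 fill the gap?** If it applies, graded on bilirubin, grade 2 gives interrupt and restart at the same dose, grade 3 gives interrupt and next lower dose, and grade 4 gives discontinue. These match the first actions of the bilirubin rows. Three details are lost: dose reduction when grade 2 takes more than 21 and up to 28 days to resolve; discontinuation on any recurrence after grade 3 (Table 6-37 allows a further reduction if the recurrence is grade 2); and twice-weekly liver tests for two weeks after restart.

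**Does Section 6.3.3.1 fill it?** At normal baseline its work-up for drug-induced liver injury starts at ALT >3 with bilirubin >2 and makes no exception for cholestasis. Every normal-baseline cholestatic case is therefore covered for work-up. The sub-threshold pattern is not. At normal baseline it stays at or below 3. For b above 1 the ALT trigger is min(3b, 8), which is never below min(max(3, 2b), 8), the top of the gap. The section sets no ribociclib dose in either case.

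**The case against.** The strongest reply is that the protocol already protects these patients.

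- Section 6.3.1 sends unlisted events to Table 6-37, whose first actions agree with the bilirubin rows, and its worst-toxicity sentence points to the bilirubin grade.
- The note under the bilirubin rows gives a first step for a cholestatic picture, and Section 6.3.3.1 adds a work-up.
- If the causal drug cannot be identified, both drugs' rules apply. Table 6-6 interrupts spartalizumab at grade 2 and stops it permanently at grade 3 or 4.
- Section 7.1.5 lets the investigator stop treatment. Interrupted subjects are seen weekly (Section 6.3.3), and a ribociclib interruption beyond 28 days for ribociclib-related toxicity forces discontinuation (Section 6.3.1.2).

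Most of this stands and limits the weight of the point, but it does not settle the ribociclib dose. Whether a combined hepatic rise counts as unlisted can be argued either way, because Table 6-2 does list hepatic events. The worst-toxicity sentence does not say which row to use when that row's heading excludes the case. Table 6-6 governs spartalizumab only.

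A reader might also infer that the three headings are mutually exclusive. They are not. With ALT/AST unchanged and bilirubin above 1 and up to 2 x ULN, both the bilirubin block and the same-grade ALT/AST row fit. Above 1.5 x ULN they prescribe different dose actions. The defect is therefore a gap in some places and an overlap in others.

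**Conclusion.** The point holds and is minor. When ALT/AST rises above baseline, Table 6-35 has no row for bilirubin above 2 x ULN with ALT/AST below the combined threshold, nor for a normal-baseline rise above the combined thresholds with cholestasis. For bilirubin above 1.5 to 2.0 x ULN, the literal reading gives a milder action when ALT/AST has also risen to grade 1 or within its baseline grade than the bilirubin rows give for that bilirubin alone. When ALT/AST is unchanged, two rows conflict.

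A reader might infer that the protocol orders dosing to continue at bilirubin of, say, 11 x ULN. It does not: the table is silent there, and Table 6-37, if it applies, means discontinuation. Nor are subjects left unprotected, given the safeguards above.

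Reach is small. Section 4.1.1 records that arm 4 enrolment stopped at 44 subjects and that the arm was declared futile. Only subjects still on ribociclib (number not given) and any later ribociclib cohort, which Section 2.3.4 leaves open, are affected. No endpoint, decision rule or efficacy analysis changes. The conclusion rests on reading the headings as written and on grading by the printed ULN multiples.

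**What to change.** Add one footnote to Table 6-35, modelled on Table 6-27 footnote b rather than Table 6-15 footnote d, which omits the bilirubin rows. Suggested text:

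*When AST/ALT and total bilirubin are both raised but the combined row does not apply (thresholds not met, or cholestasis), or when rows from both blocks fit, apply both the bilirubin rows and the AST/ALT rows regardless of the 'without' headings and take the more conservative action, after excluding alternative causes as described in the note to the bilirubin rows.*

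Once other causes are excluded, the test cases resolve as follows. Baseline ALT 0.8, ALT 2.5, bilirubin 1.8: interrupt. The same ALT with bilirubin 5, baseline ALT 4 with ALT 6 and bilirubin 5, and baseline ALT 0.8 with ALT 5, bilirubin 4 and cholestasis: interrupt, next lower dose, discontinue on recurrence. The overlap at bilirubin 1.8 with unchanged ALT: interrupt.

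The cost is one footnote in the next amendment. The sub-threshold part can be adapted from Table 6-27. The wording on cholestasis, overlap and headings is new, because neither existing footnote expressly covers a cholestatic rise above the thresholds.
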